- **Protocol number:** 331-10-238.
- **Document title:** A Long-term, Phase 3, Multicenter, Open-label Trial to Evaluate the Safety and Tolerability of Oral OPC-34712 as Adjunctive Therapy in Adults with Major Depressive Disorder, the Orion Trial.
- **Version number:** Amendment 4.
- **Date of the document:** 13 Jun 2014.
- **NCT number:** NCT01360866.

Otsuka Pharmaceutical
Development & Commercialization, Inc.

Investigational Medicinal Product

Brexipiprazole (OPC-34712)

REVISED CLINICAL PROTOCOL

A Long-term, Phase 3, Multicenter, Open-label Trial to Evaluate the Safety and
Tolerability of Oral OPC-34712 as Adjunctive Therapy in Adults with Major Depressive
Disorder, the Orion Trial

Protocol No. 331-10-238

IND No. 103,958

EudraCT No. 2011-001351-37

CONFIDENTIAL – PROPRIETARY INFORMATION

Drug Development Phase: 3

Sponsor: Otsuka Pharmaceutical Development &
Commercialization, Inc.
[name]
[name]

Sponsor Representatives:

[REDACTED]

Phone

Fax

E-mail

[REDACTED]

Phone

Fax

E-mail

[REDACTED]

Phone

Fax

E-mail

Immediately Reportable Event

INC Research (see [Appendix 2](#))

Issue Date: 11 May 2011

Date of Amendment 1: 23 Nov 2011

Date of Amendment 2: 16 Nov 2012

Date of Amendment 3: 11 Apr 2014

Date of Amendment 4: 13 Jun 2014

Protocol Synopsis

Name of Company: Otsuka Pharmaceutical Development & Commercialization, Inc.	Protocol #331-10-238 IND #103,958 EudraCT #2011-001351-37
Protocol Title:	A Long-term, Phase 3, Multicenter, Open-label Trial to Evaluate the Safety and Tolerability of Oral OPC-34712 as Adjunctive Therapy in Adults with Major Depressive Disorder, the Orion Trial
Clinical Phase:	3
Treatment Indication:	Major Depressive Disorder (MDD)
Objective(s):	
Primary: To assess the long-term safety and tolerability of oral OPC-34712 (hereafter referred to by the generic name “brexpiprazole”) as adjunctive therapy in the treatment of adults with MDD.
 
Secondary: To assess the long-term efficacy of oral brexpiprazole as adjunctive therapy in the treatment of adults with MDD.

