^bIf a subject discontinues prematurely before Week 26, procedures noted for Week 26 must be completed at the early termination (ET) visit. Subjects who have completed 26 weeks or more, will have the Week 26/ET procedures at their next scheduled visit.

^cConsists of telephone contact or clinic visit (investigator's discretion) for evaluation of safety and applies to all subjects (completers and early withdrawals).

^dInformed consent for Trial 331-10-238 will occur at Screening/Baseline and must be obtained before any trial-related procedures specific to the open-label trial are performed.

^eUpdate, if necessary.

^fImprovement should be based on the subject's status at the last scheduled visit of the prior double-blind phase 3 trial.

^gVital signs include body weight, body temperature, systolic blood pressure (SBP), diastolic blood pressure (DBP), and heart rate. Blood pressure and heart rate will be measured in the following order: supine, sitting, and standing after the subject has been in each position for at least 3 minutes. Vital signs scheduled for the same visit as blood samples are to be completed before blood is drawn.

^hStandard 12-lead ECGs will be performed after the subject has been supine and at rest for \geq 5 minutes prior to the ECG. A central ECG service will be utilized to review all ECGs in order to standardize interpretations for the safety analysis. In addition, ECG results will be evaluated at the investigational site to monitor safety during the trial. Subjects will be enrolled in Trial 331-10-238 based on the screening/baseline ECG results from the trial site. If the screening/baseline ECG results from the central reader (ie, the last scheduled visit of the prior double-blind phase 3 trial), when available, indicate a QTcF

≥ 450 msec at screening/baseline, the investigator must contact the medical monitor to discuss the subject's continued participation in the trial. ECGs scheduled for the same visit as blood samples are to be completed before blood is drawn.

ⁱIncludes hematology (including PT, aPTT, and INR), serum chemistry (including prolactin and TSH, with reflex to free thyroxine [T₄] if the result for TSH is abnormal), and urinalysis.

^jSubjects must be fasting for a minimum of 8 hours prior to blood draws for screening/baseline laboratory assessments (ie, the last scheduled visit of the prior double-blind phase 3 trial).

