3.6.1.8 End of Treatment (Week 26/ET)

The Week 26 visit signifies the end of treatment. Therefore, all subjects will undergo a complete evaluation at Week 26 (\pm 2 days). In addition, Week 26 evaluations are to be completed, if possible, for any subject withdrawn from the trial prematurely. Since the original 52 week open-label trial design has been modified as a part of Amendment 3 to shorten the duration of the trial to 26 weeks, ongoing subjects who have not reached their Week 26 visit will be re-consented and will follow Amendment 3 schedule of assessments. Ongoing subjects who have already completed their Week 26 visit at the time Amendment 3 is approved will follow Amendment 3 week 26/ET schedule of assessments at their next scheduled visit. The following activities and assessments will occur at Week 26 (or at the ET visit, if applicable):

- The investigator (or qualified designee) will administer the CGI-S and CGI-I.

- An adequately trained and experienced clinician will administer the SAS, AIMS, and BARS to assess EPS.
- The investigator (or qualified designee) will complete the “Since Last Visit” C-SSRS form.
- The subject will complete the MSFQ, SDS, IDS-SR, and the Follow-up RUF.
- A complete physical examination (including waist circumference) will be performed.
- Vital sign measurements (body weight, body temperature, blood pressure, and heart rate) will be recorded. Blood pressure and heart rate are to be measured in the following order: supine, sitting, and standing after the subject has been in each position at least 3 minutes. Vital signs are to be completed before any blood is drawn.
- A standard 12-lead ECG will be performed after the subject has been supine and at rest for at least 5 minutes. The ECG is to be completed before any blood is drawn.
- A fasting blood draw will be collected for clinical laboratory tests (hematology, including PT, aPTT, and INR; and serum chemistry, including prolactin, HbA1c, and TSH, with reflex to free T₄ if TSH is abnormal). Vital sign and ECG assessments should be completed before any blood samples are collected.
- Samples will be obtained for blood alcohol testing.
- Urine will be collected for urinalysis and urine screen(s) for drugs of abuse.
- WOCBP will be given a urine pregnancy test. Any positive result must be confirmed by a serum pregnancy test.
- Final drug accountability will be performed.

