3.6.1.9 Follow-up

Follow-up safety information (AEs and concomitant medications) will be collected 30 (+ 2) days after the last dose of open-label medication for all subjects (completers and early withdrawals). Follow-up information can be obtained via telephone contact or clinic visit at the investigator’s discretion.

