5.1 Data Sets Analyzed

The following datasets are defined for this study:

- Enrolled Sample: comprises all subjects who sign an ICF for the trial.
- Safety Sample: comprises those subjects who receive at least one dose of open-label brexpiprazole as adjunctive therapy to one of the allowed ADTs.
- Efficacy Sample: comprises those subjects in the Safety Sample who have at least one post-baseline efficacy evaluation of CGI-S.

All the summaries will be done for all subjects, 52-week enrollers (before Protocol Amendment 3), and 26-week enrollers (after Protocol Amendment 3), and will be done by parent study treatment group. Selected summaries will also be done by ADT. Details of those summaries will be specified in the following sections.

The Safety Sample will be used for all baseline and safety summaries. The Efficacy Sample will be used for the efficacy summaries.

The observed case (OC) dataset will consist of the actual observations recorded at each visit and will be used to present summaries per trial week.

The last-observation-carried-forward (LOCF) data set will include data recorded at a given visit in the Treatment Phase or, if no observation is recorded at that visit, data carried forward from the previous visit in the Treatment Phase. Data collected prior to or on the first day of Treatment Phase dosing will not be carried forward or averaged with Treatment Phase data to impute missing values for the LOCF data set.

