9.1 Adverse Events

All AEs will be coded by Medical Dictionary for Regulatory Activities (MedDRA) system organ class and preferred term. The incidence of the following events will be summarized:

- TEAEs by severity
- Potentially drug-related TEAEs
- TEAEs with an outcome of death
- Serious TEAEs
- Discontinuations due to TEAEs

A TEAE is defined as an AE that starts after the first dose of IMP or an AE that is reported at baseline and increases in intensity or becomes serious or trial drug-related or results in death, discontinuation, interruption or reduction of IMP.

In addition, incidence of TEAE during Treatment Phase of at least 5% by SOC and PT will be provided.

Incidence of TEAEs by SOC and PT will be summarized for sex, race and age subgroups.

EPS-related AEs will be grouped into five categories.

- 1) Dystonic Events, which include cervical spasm, dystonia, emprosthotonus, muscle contractions involuntary, muscle rigidity, muscle spasms, muscle spasticity, myotonia, nuchal rigidity, oculogyration, opisthotonus, pleurothotonus, risus sardonicus, torticollis, and trismus;
- 2) Parkinsonian Events, which include akinesia, asterixis, athetosis, bradykinesia, cogwheel rigidity, essential tremor, extrapyramidal disorder, freezing phenomenon, gait festinating, hypertonia, hypokinesia, hypokinesia neonatal, intention tremor, masked facies, parkinson's disease, parkinsonian crisis, parkinsonian gait, parkinsonian rest tremor, parkinsonism, tremor, and tremor neonatal;
- 3) Akathisia Events, which include akathisia, hyperkinesia, and psychomotor hyperactivity;
- 4) Dyskinetic Events, which include ballismus, buccoglossal syndrome, choreoathetosis, clumsiness, dyskinesia, dyskinesia neonatal, dyskinesia oesophageal, fumbling, nodding of head, on and off phenomenon, and tardive dyskinesia;
- 5) Residual Events, which include chorea, huntington's chorea, muscle twitching, and myoclonus.

Incidence of EPS-related TEAEs will be summarized by EPS category. This summary will also be provided by ADT.

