11.2.8 Resource Utilization Scale

The Resource Utilization Form is a self-report tool designed to collect information regarding the extent of medical care sought by patients while participating in the study. Incidence rates (related to number of visits to a health care provider, number of times hospitalized, or number of days hospitalized) will be expressed through the average use per person-year. For each group, the number of events across all patients in that group will be divided by the total person year (study duration in days / 365.25) during the open-label study across all patients.

12 Appendices

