- CT-8.6.3.2 Incidence of Treatment-emergent Adverse Events Resulting in Discontinuation from Study Medication by System Organ Class, MedDRA Preferred Term and Severity – 52-Week Enrollers
- CT-8.6.3.3 Incidence of Treatment-emergent Adverse Events Resulting in Discontinuation from Study Medication by System Organ Class, MedDRA Preferred Term and Severity – 26-Week Enrollers
- CT-8.7.1 Incidence of TEAE Occurring in at Least 5 Percent of Patients by System Organ Class and MedDRA Preferred Term in the Total Group – All Subjects
- CT-8.7.2 Incidence of TEAE Occurring in at Least 5 Percent of Patients by System Organ Class and MedDRA Preferred Term in the Total Group – 52-Week Enrollers
- CT-8.7.3 Incidence of TEAE Occurring in at Least 5 Percent of Patients by System Organ Class and MedDRA Preferred Term in the Total Group – 26-Week Enrollers
- CT-8.8.1.1 Incidence of TE EPS-related AEs by EPS Category and MedDRA Preferred Term – All Subjects
- CT-8.8.1.2 Incidence of TE EPS-related AEs by EPS Category and MedDRA Preferred Term – 52-Week Enrollers
- CT-8.8.1.3 Incidence of TE EPS-related AEs by EPS Category and MedDRA Preferred Term – 26-Week Enrollers
- CT-8.8.2.1 Incidence of TE EPS-related AEs by EPS Category and MedDRA Preferred Term by ADT – All Subjects
- CT-8.8.2.2 Incidence of TE EPS-related AEs by EPS Category and MedDRA Preferred Term by ADT – 52-Week Enrollers
- CT-8.8.2.3 Incidence of TE EPS-related AEs by EPS Category and MedDRA Preferred Term by ADT – 26-Week Enrollers

CT-9.1 Listing of Deaths

CT-9.2.1 Listing of Serious Adverse Events – All Subjects

CT-9.2.2 Listing of Serious Adverse Events – 52-Week Enrollers

CT-9.2.3 Listing of Serious Adverse Events – 26-Week Enrollers

CT-9.3.1 Listing of Discontinuations from Study Medication Due to Adverse Events – All Subjects

CT-9.3.2 Listing of Discontinuations from Study Medication Due to Adverse Events – 52-Week Enrollers

CT-9.3.3 Listing of Discontinuations from Study Medication Due to Adverse Events – 26-Week Enrollers

CT-10.1.1.1 Mean Change from Baseline in Clinical Laboratory Test Results - Serum Chemistry – All Subjects

CT-10.1.1.2 Mean Change from Baseline in Clinical Laboratory Test Results - Serum Chemistry – 52-Week Enrollers

CT-10.1.1.3 Mean Change from Baseline in Clinical Laboratory Test Results - Serum Chemistry – 26-Week Enrollers

CT-10.1.2.1 Mean Change from Baseline in Clinical Laboratory Test Results - Hematology – All Subjects

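### Crude TEAE incidence in the 52-week-enroller and All Subjects tables pools planned follow-up of 26 to 52 weeks, with no common time horizon

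*SAP*

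**What the plan says.** **Reporting groups.** SAP 5.1 splits every summary by enrolment relative to Amendment 3: "All the summaries will be done for all subjects, 52-week enrollers (before Protocol Amendment 3), and 26-week enrollers (after Protocol Amendment 3"). SAP 13 lists these as three separate tables for almost every output. SAP 3.1.1 and 3.1.2 describe one 52-week design and one 26-week design. They do not mention subjects who started under the first and were moved to the second.

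**Transition rule.** This is only in the protocol. Section 3.6.1.8 says that "ongoing subjects who have not reached their Week 26 visit will be re-consented and will follow Amendment 3 schedule of assessments". For the rest, Table 3.6-1 footnote b says: "Subjects who have completed 26 weeks or more, will have the Week 26/ET procedures at their next scheduled visit". The title page gives "Date of Amendment 3: 11 Apr 2014".

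**TEAEs.** SAP 9.1 reports the incidence of TEAEs, serious TEAEs and discontinuations due to TEAEs. The definition gives a start, "A TEAE is defined as an AE that starts after the first dose of IMP", but no end. The at-least-5% summary is the exception, because SAP 9.1 confines it to the Treatment Phase. Protocol 3.6.1.9 extends collection beyond treatment: "Follow-up safety information (AEs and concomitant medications) will be collected 30 (+ 2) days after the last dose of open-label medication".

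**Person-time.** The SAP uses it only for resource use (11.2.8), where "the number of events across all patients in that group will be divided by the total person year".

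**Last visit.** SAP 5.2 uses LOCF for last-visit analyses. SAP 8 defines the last visit as Week 26/ET or Week 52/ET. SAP 9.8 gives only Week 52/ET, for every group.

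**The concern.** The label 52-week enrollers suggests a group planned for 52 weeks. Under the transition rule it is not, and All Subjects then adds the 26-week enrollers. A crude percentage with an event grows with the time subjects are observed. When planned time differs for administrative reasons, the percentage depends on the calendar mix of entry dates as well as on the drug.

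The frequency and severity of AEs is the primary outcome (Protocol 3.5.1), and description is all that this trial delivers. A reader who takes the TEAE percentage in these two table sets as a one-year risk, or as a six-month risk, would be wrong either way. Comparing the 52-week-enroller tables with the 26-week-enroller tables would partly compare lengths of follow-up. The mix also affects which events enter the tables titled "Incidence of TEAE Occurring in at Least 5 Percent of Patients by System Organ Class" (CT-8.7.1 to CT-8.7.3).

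**Working it through.** The plan states no figure to reproduce: the sample size is not power-based, and no event rate is given.

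**Step 1: planned follow-up before Amendment 3.** Scheduled visits after Week 26 were Weeks 32, 38, 44 and 52. Day 1 is the first dose, so Day n = first dose + (n − 1). Assume that Amendment 3 took effect everywhere on 11 Apr 2014 and that visits fell on the target days in SAP Table 11.1-1 (Days 182, 224, 266, 308, 364).

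| First dose | Planned end | Days in band |
|---|---|---|
| 11 May 2011 to 8 Jun 2013 | Week 52 | 760 |
| 9 Jun to 20 Jul 2013 | Week 44 | 42 |
| 21 Jul to 31 Aug 2013 | Week 38 | 42 |
| 1 Sep to 12 Oct 2013 | Week 32 | 42 |
| 13 Oct 2013 to 11 Apr 2014 | Week 26 | 181 |

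The start is the protocol issue date, the earliest possible entry. The shortened bands cover 42 + 42 + 42 + 181 = 307 of 1,067 days, or 28.8%. This is a share of calendar time, not of subjects. Later approval at a site moves every date later (Protocol 13).

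**Step 2: group membership.** Read literally, SAP 5.1 puts all these subjects among the 52-week enrollers. Both that group and All Subjects then span 26 to 52 weeks. If re-consented subjects were counted as 26-week enrollers, which the SAP does not say, the ranges would be 32 to 52 and 26 to 52 weeks. The mixing remains under either reading.

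**Step 3: illustration of size (all inputs assumed).** Cumulative event hazard H(t) = λ(t/26)^k, with k = 1 (constant) or k = 0.5 (early-weighted). Dropout hazard d = −ln(1 − D)/26, where D is dropout by Week 26. Crude incidence by week t is the integral from 0 to t of H′(s)·exp(−H(s) − d·s) ds. λ is set so that the 26-week value is 4% or 10%.

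| k | D | 52-week value if 4% at Week 26 | 52-week value if 10% at Week 26 |
|---|---|---|---|
| 1 | 0% | 7.84% (ratio 1.96) | 19.0% (1.90) |
| 1 | 40% | 6.28% (1.57) | 15.2% (1.52) |
| 0.5 | 0% | 5.61% (1.40) | 13.8% (1.38) |
| 0.5 | 40% | 4.89% (1.22) | 12.1% (1.21) |

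Check of the first row: 1 − 0.96² = 7.84%. The ratio runs from about 1.2 to 2.0. A mixed group lies between its 26-week and 52-week values. For the 5% threshold, with constant hazard and no dropout, a 26-week risk of 1 − √0.95 = 2.53% reaches 5% at 52 weeks.

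**Step 4: would patient-years alone solve it?** For the 4% event without dropout, first events per 100 patient-years at 26 and 52 weeks are 8.2 and 8.2 if k = 1, but about 8.2 and 5.8 if k = 0.5. The rate removes the mix effect only when the hazard is roughly constant.

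**The case against.** The strongest reply is that the SAP already gives much of what is needed. It separates the enrolment groups into their own tables, summarises the scales by week on observed cases including Week 26, shows weight abnormalities by visit (CT-11.2.2.1 to CT-11.2.2.3), and reports completion by week and exposure by 4-week interval. The trial has no comparator and no test, and the SAP plans no contrast between the enrolment groups. Protocol 7.1.4 asks for the last visit, not for a fixed-week estimate.

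Most of this stands and limits the point. None of it supplies a TEAE incidence at a common time, which is the primary output.

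The reply also disposes of some stronger readings that a reader might infer:

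- That no TEAE table has a stated end. This is not so: the at-least-5% summary stops at the end of the Treatment Phase. That phase still varies in length, and the other TEAE tables state no end.
- That the last-visit LOCF values cannot be interpreted. For the rating scales, SAP 11.1 drops evaluations more than seven days after the last dose, so these are last on-treatment values, and the observed-case Week 26 summary provides a common time point.
- That the 26-week-enroller tables suffer the same defect. They have one planned duration. Post-treatment collection leaves their end day unstated in most TEAE tables, but the documents give no post-dose event rate from which to size this, and early withdrawals receive the same follow-up contact.

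**Conclusion.** The point holds, as one of interpretation. That planned follow-up is mixed follows directly from the protocol's transition rule and the grouping in SAP 5.1, and does not depend on any assumption about rates. Crude TEAE incidence in the 52-week-enroller and All Subjects tables is then tied to no single time horizon. The LOCF last-visit issue is real but secondary.

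The size cannot be known from the documents, which give no event rates, dropout or enrolment by date. The ratio of about 1.2 to 2.0 rests on assumed hazards, assumed dropout and the simplification that AE observation ends at dropout. Its upper end needs a constant hazard and no dropout. It compares full 52-week with 26-week follow-up, so the distortion in a mixed table would be smaller. A reader might infer that an error rate or a formal comparison is compromised; the plan contains neither, so nothing of that kind follows.

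**What to change.** 1. In all three table sets, add the incidence of TEAEs, serious TEAEs and discontinuations due to TEAEs with onset from first dose through Day 182. This gives a common horizon; it does not adjust for dropout.
2. For last-visit summaries of visit-based measures, including weight, add a version using data through Day 203. That is the end of the Week 26 window: it keeps Week 26 visits made up to two days late (Day 184) and excludes Week 32 visits, whose window opens on Day 204. State that this window applies to weight, because SAP 11.1 names only the rating scales.
3. As a supplement, give subjects with a first event per 100 patient-years, extending the approach of SAP 11.2.8. State where observation ends, and note that the rate removes the mix effect only if the hazard is roughly constant.
4. Put the transition rule into the SAP, say to which group re-consented subjects belong, and make the Week 52/ET label in SAP 9.8 consistent with SAP 8.

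This is a cheap improvement: SAP wording and extra summaries from data already collected, with no protocol amendment. The downside is longer tables.

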5.2 Handling of Missing Data

In order to assess sensitivity of results due to missing data, 2 types of analyses will be performed: LOCF and OC. The OC dataset will consist of the actual observations recorded at each visit. The LOCF dataset will include data recorded at a scheduled visit, i.e., all OC data, or, if no observation is recorded at that visit, data carried forward from the previously scheduled visit. Baseline data will not be carried forward to impute missing values for the LOCF dataset. The OC data set will be used for analyses at each study visit and the LOCF data set will be used for analyses at the last visit.

6 Study Conduct

6.1 Subject Disposition, Completion Rate and Reasons for Discontinuation

Subject disposition will be summarized for the Enrolled Sample.

Subject completion rate by week, and reasons for discontinuation will be summarized for the Enrolled Sample. In addition, these summaries will also be done by ADT

6.2 Treatment Compliance

Treatment compliance will be reported, by percentage of patients taking investigational medicinal product based on investigational medicinal product (IMP) panel of the case report form (CRF).

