3.11 Subject Compliance

Responsible trial personnel will dispense the IMP (ie, brexpiprazole and ADTs). Accountability and compliance verification should be documented in the subject’s trial records. Subjects must be counseled on the importance of taking the IMP as directed at all trial visits. If poor compliance continues (eg, multiple missed doses resulting in less than 80% overall compliance at any point in the trial), discontinuation of the subject from the trial should be considered. Subjects who habitually miss visits or habitually attend visits outside of the protocol-defined visit window are also noncompliant and should be considered for discontinuation. The medical monitor should be contacted if the investigator is uncertain whether a subject’s lack of compliance merits discontinuation from the trial.

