8.1 Packaging and Labeling

Trial drugs will be provided to the investigator(s) by the sponsor (or designated agent). The IMP will consist of open-label brexpiprazole and open-label ADTs. Open-label brexpiprazole will be supplied as 0.5, 1, 2, and 3-mg tablets packaged in weekly blister cards, each containing sufficient tablets for 7 (+ 2 days). Blister cards will contain single tablet strengths (ie, brexpiprazole 0.5, 1, 2, or 3 mg/day) and subjects will take 1 tablet daily. When accessed by the site, the IVRS or IWRS will assign a specific blister card number to be dispensed to a subject. New weekly blister cards will be dispensed at each scheduled visit and at unscheduled visits if the dose of brexpiprazole is changed.

Each blister card used in the trial will be given an identifying number and will be labeled to clearly disclose the blister card number, Subject ID (to be filled in by the site staff/investigator), subject's initials or other unique identifier, name of the investigator (to be filled in by the site staff/investigator), site number (to be filled in by the site staff/investigator), subject's initials (to be filled in by the site staff/investigator), date dispensed (to be filled in by the site staff/investigator), compound ID, protocol number, the sponsor's name and address, instructions for use, route of administration, and appropriate precautionary statements. Once a blister card has been assigned to a subject via the IVRS or IWRS, it cannot be dispensed to another subject.

ADTs will be supplied as bulk drug in commercial packaging (eg, bottles) with an ancillary trial-specific label that will be positioned such that it will not obscure the original commercial label. The sponsor reserves the right to use a generic equivalent, should any marketed antidepressant become unavailable during the course of the trial. Each ADT bottle used in the trial will be labeled to clearly disclose the bottle number, Subject ID, subject's initials, protocol number, ADT drug name, the sponsor's name and address, instructions for use, route of administration, and appropriate precautionary statements. Once an ADT bottle has been assigned to a subject via the IVRS or IWRS, it cannot be dispensed to another subject. The amount of open-label ADT dispensed to a subject at each visit will be contingent upon the prescribed daily dose of ADT as well as the duration between trial visits. Subjects must remain on the same ADT for the duration

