8.3 Accountability

The investigator, or designee, must maintain an inventory record of trial drugs (including brexpiprazole and ADTs) received, dispensed, administered, and returned.

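### SAP 6.2 reports compliance as a share of patients, with no denominator, interval or drug named, so it cannot show what share of assigned doses was taken

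*SAP*

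**What the plan says.** SAP 6.2 states: "Treatment compliance will be reported, by percentage of patients taking investigational medicinal product", and gives the IMP panel of the CRF as the source. It does not say over which sample, over what period, or for which drug.

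The protocol uses the word differently. Protocol 3.11 asks sites to consider discontinuing a subject whose poor compliance persists, and gives as an example "multiple missed doses resulting in less than 80% overall compliance at any point in the trial". That is a share of doses within one subject.

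Three other provisions bear on the point:

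- **Denominator.** SAP 5.1 offers two candidates. One is "Safety Sample: comprises those subjects who receive at least one dose of open-label brexpiprazole as adjunctive therapy to one of the allowed ADTs"; the other is "Enrolled Sample: comprises all subjects who sign an ICF for the trial".
- **Drug.** The protocol's definition of IMP, repeated in Protocol 8.1, covers both brexpiprazole and the ADT.
- **Dose counting.** Each brexpiprazole blister card holds a single strength and "subjects will take 1 tablet daily" (Protocol 8.1). Under Protocol 8.3 the site "must maintain an inventory record of trial drugs (including brexpiprazole and ADTs) received, dispensed, administered, and returned". Table 3.6-1 schedules IMP accountability at every treatment visit after baseline.

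**The concern.** A count of people cannot stand in for a count of doses. A subject who misses a third of the tablets and one who misses none contribute equally to the SAP 6.2 figure.

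The primary objective is long-term safety and tolerability in outpatients who, from Week 8 on, are seen only every six weeks. Anyone reading the adverse event, weight, prolactin or QTc results will want to know how fully the assigned treatment was taken. The compliance section is where they would look, and the planned statistic does not tell them. Nor does it show how many subjects fell below the level that the protocol itself uses to illustrate poor compliance.

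**Working it through.** The plan states no compliance figure, so there is nothing to reproduce. The check is what SAP 6.2 returns under each possible reading, and whether another section supplies what is missing.

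**Readings of SAP 6.2**

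1. *Ever took IMP, Safety Sample.* Membership requires at least one dose, so the result is exactly 100% whatever the rate of missed doses.
2. *Took IMP in a 4-week interval, subjects still on treatment.* If tablets are taken independently each day with probability p, the chance of at least one dose in 28 days is 1 − (1 − p)^28. At p = 0.2 this is 1 − 0.8^28 = 0.998. A subject taking one tablet in five is almost always counted as taking IMP.
3. *Ever took IMP, Enrolled Sample.* The result is 100% minus the share who sign consent but never start. The documents give no rate; an assumed 0–15% gives 85–100%. This measures screen failure.
4. *Taking IMP by week, fixed Safety Sample denominator.* Assumed dropout of 20–40% by Week 26 gives 80–60%. This measures retention, which SAP 6.1 already reports as completion rate by week.

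**Comparison with a dose-based measure**

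Assumptions: 1,000 treated subjects, 26 × 7 = 182 daily tablets, independent daily intake with probability p, and no dropout. The 80% line is 0.80 × 182 = 145.6, so a subject needs at least 146 tablets.

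| p | Ever taking IMP | Lowest 4-week interval | Tablets taken / expected | Subjects at or above 80% |
|---|---|---|---|---|
| 0.9 | 100% | 100% | 90% | 100% |
| 0.8 | 100% | 100% | 80% | 51.5% |
| 0.6 | 100% | 100% | 60% | 0% |
| 0.4 | 100% | 100% | 40% | 0% |
| 0.2 | 100% | 99.5% | 20% | 0% |

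The exact binomial probability of at least 146 of 182 tablets at p = 0.8 is also 51.5%. The two patient-count columns hardly move while intake falls from 90% to 20%. Independent daily intake is a simplification. Long unbroken gaps would lower the 4-week column, but reading 1 does not depend on this assumption.

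**Other sections**

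- SAP 9.7 counts patients receiving brexpiprazole, and each dose level, by 4-week interval. It gives dose level, not the fraction taken.
- SAP 6.3 summarises dosing deviations by type and lists them by subject, with no denominator of expected doses.
- SAP 6.1 tabulates reasons for discontinuation, which could show only subjects who left.
- The proposed table list in SAP 13 contains no compliance table.

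**The case against.** The strongest reply is that SAP 6.2 is merely underspecified and that little depends on it. Much of this stands.

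- *A reader might infer that the figure is near 100% by construction.* The text does not support that in general. It is exact for ever-treated members of the Safety Sample, but SAP 6.2 names no denominator. Over the Enrolled Sample, or by week over a fixed denominator, the figure could be well below 100%. It would then measure something other than adherence.
- *A reader might infer that missed tablets cause safety findings to be credited to too high a dose.* A subject assigned 3 mg/day who takes 70% of tablets does average 0.70 × 3 = 2.1 mg/day. But dosing is flexible, and no safety outcome is tabulated by brexpiprazole dose. Summaries are by parent-study treatment, enrolment cohort and, for some, ADT, sex, race or age. Dose level appears only in the exposure tables CT-7.1.3 and CT-7.1.4.
- *A reader might infer that a subject who stops brexpiprazole but continues the ADT goes unseen.* SAP 6.2 is ambiguous on the drug, but SAP 9.7 reports brexpiprazole and ADT exposure separately, so such a subject should be visible there.
- *A reader might infer that the SAP replaces a compliance analysis defined in the protocol.* It does not. The 80% figure is an example in a rule on trial conduct, and Protocol Section 7 plans no compliance analysis.
- *The IMP panel is not in the documents.* Whether it holds tablet counts, missed days or only start and stop dates is unknown.
- *The missing table is weak evidence.* The SAP 13 list is headed as proposed, and it also lacks the protocol-deviation table that SAP 6.3 promises.

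What remains is that the one statistic named as compliance is a percentage of patients. Naming its denominator, interval and drug would clarify it but would not turn it into a measure of doses taken.

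**Conclusion.** The point holds in limited form. As written, SAP 6.2 cannot report the share of assigned doses taken or the number of subjects below 80%, and no other SAP section does. This follows from the wording and needs no assumed rate. The simulated figures only illustrate the size of the blind spot: intake from 40% to 90% gives the same 100%.

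The consequence is confined to interpreting exposure and adherence behind descriptive long-term safety results. No test, sample size or dose-specific safety table depends on it. The change is worth making because the present statistic does not measure what its section title promises and a standard one is readily defined. The conclusion assumes that SAP 6.2 means what it says. If the IMP panel records tablets or missed days, that makes the fix easier but does not alter the statistic as specified.

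**What to change.** Rewrite SAP 6.2 as follows:

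- **Measure.** For each Safety Sample subject, brexpiprazole compliance = tablets taken / tablets expected. Expected is one tablet per day from first to last dose, allowing for recorded interruptions. Because each card holds one strength taken once daily, changes of dose level do not affect the count.
- **Source.** The IMP panel of the CRF, or accountability data already in the database.
- **Reporting.** Mean, median, and number and percentage of subjects below 80%, overall and by parent-study treatment group, for the three cohorts in SAP 5.1 (all subjects, 52-week enrollers, 26-week enrollers). Add the tables to SAP 13.
- **ADT.** Report separately, and only where the data allow, as days dosed over days expected. Strengths vary and some ADTs may be taken once or twice daily, so a tablet or capsule count per day would mislead.

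The cost is SAP wording and one table repeated for the three cohorts. There are two downsides. The reported figure will probably look less favourable. And tablet counts may not be in the database, since Protocol 8.3 describes a site inventory record. In that case, base compliance on dosing days recorded in the IMP panel and state the limitation. With up to about 3,000 subjects planned in Protocol 7.2, retrospective collection from sites is not justified for this purpose.
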